Comparison of Aerosol Delivery of Infasurf to Usual Care in Spontaneously Breathing RDS Patients.

Executive Summary:

Rationale: Surfactant replacement therapy can be life saving for newborn infants born with symptomatic lung surfactant deficiency causing Respiratory Distress Syndrome (RDS). Currently such therapy requires instillation of a liquid suspension into the trachea through an endotracheal tube. Prolonged endotracheal intubation or repeated re-intubations have undesirable adverse effects on fragile premature infants. Instilling surfactant as liquid suspension into the lung is associated with adverse events due to interruption of breathing in patients who already have respiratory insufficiency. Effective aerosol delivery of Infasurf to such patients could decrease the incidence and length of endotracheal intubation and decrease the incidence and severity of adverse events during surfactant administration.

Design: This prospective, randomized, multicenter, unblinded clinical trial will compare “usual care” to aerosolized Infasurf. The study objective is to document that aerosolized Infasurf is superior to “usual care” and provides for some patients effective surfactant therapy with less need for endotracheal intubation and instillation of a surfactant suspension into the airway. Two cohorts will be recruited: (a) patients who did not receive surfactant at birth who develop RDS in the first hours of life and (b) patients who received instillation of surfactant for RDS in the first hour of life, were extubated, and have continuing RDS.

TABLE OF CONTENTS

1. GENERAL INFORMATION	2
2. BACKGROUND INFORMATION	2
3. OBJECTIVES AND PURPOSES OF THE TRIAL	3
4. TRIAL DESIGN	4
5. SELECTION AND WITHDRAWAL OF SUBJECTS	6
6. TREATMENT OF SUBJECTS	7
7. ASSESSMENT OF EFFICACY	8
8. ASSESSMENT OF SAFETY	9
9. STATISTICS	10
10. ACCESS TO DATA	12
11. QUALITY ASSURANCE & QUALITY CONTROL	12
12. ETHICS	13
13. DATA HANDLING AND RECORD KEEPING	13
14. PUBLICATIONS	14
15. APPENDIX	14
16. REFERENCES	19

1. GENERAL INFORMATION

Version1.3
3/25/2020

1.1 Study Title *Comparison of Aerosol Infasurf to Usual Care for Respiratory Distress Syndrome (RDS)*

1.6 Principal Investigators: To be selected

1.7 Description

This is a pivotal clinical trial to determine whether Infasurf aerosolized into the oropharynx using a Solarys® aerosol generator adapted for neonatal use is superior to “usual care” for non-intubated, spontaneously breathing patients with mild RDS. This alternative method of delivery may benefit some patients by supplying sufficient Infasurf to avoid endotracheal intubation and intratracheal instillation of a surfactant suspension. Patients who have not received surfactant in the first hour of age and patients who received intratracheal surfactant in the first hour after birth but were subsequently extubated will be eligible to participate. Treatment will not be masked. All data will be extracted from the medical record for the first 28 days of life or until hospital discharge, whichever occurs first.

2. BACKGROUND INFORMATION

2.1 Test Drug & Test Device

Infasurf® (calfactant) Intratracheal Suspension for intratracheal use only is an FDA approved drug for the prevention and treatment of the Respiratory Distress Syndrome (RDS). It has no contraindications. It has no identified toxicity. Administration of Infasurf is associated with occasional complications of cyanosis, alterations in heart rate and blood pressure, airway obstruction and reflux of the surfactant. Currently, administration of Infasurf requires endotracheal intubation for intratracheal instillation.

The Solarys® aerosol generator is an FDA approved medical device for delivery of aerosolized drugs to the lungs of intubated patients. The proximal tip of the device has been imbedded in a pacifier shaped adaptation so the Infasurf aerosol can be delivered into the oropharynx and not into the respiratory support air flow at the nares.

2.2 Preclinical

Studies have been conducted in surfactant deficient premature lambs in which Infasurf has been aerosolized, rather than instilled, into the lung through the endotracheal tube. In some lambs, those with moderate respiratory dysfunction, the aerosolized Infasurf was able to significantly improve respiratory function. Premature lambs with RDS do not spontaneously breathe.

Additional studies have been done in full term, healthy newborn lambs in which the aerosolized Infasurf was delivered into the upper airway above the larynx. No physiologic benefit was observed (the animals were healthy) but a sufficient fraction of the Infasurf was inhaled into the lung to predict a positive beneficial effect in symptomatic individuals. These animal studies have not yet been presented at scientific meetings or published.

2.3 Potential Risks

It is possible that some patients will have their respiratory status worsen when aerosolized Infasurf is administered because of physical interference with ventilation. Constant, direct monitoring of the patients by health care professionals during the aerosolization is included in the protocol so that such events will be immediately recognized, the aerosolization discontinued and appropriate interventions immediately implemented to restore optimal breathing. Pilot studies of over 30 patients resulted in no patient developing interference with breathing that required discontinuation of the aerosolization.

Infasurf is unchanged in any way by aerosolization. Aerosolized Infasurf deposits only in the lung (the site of its activity) or in the stomach. There are no additional risks from Infasurf delivered as an aerosol than there are from Infasurf when instilled into the lung.

2.4 Potential Benefits

Successful administration of Infasurf by aerosolization will provide two important benefits for patients. (1) Endotracheal intubation (or endotracheal re-intubation) may be able to be avoided in some patients, and (2) the adverse events at instillation due to filling the airway with liquid and interrupting breathing may be diminished or abolished.

2.5 Justification

The dose aerosolized will be up to twice the dose currently instilled which is 3 ml/kg body weight (105 mg phospholipid/kg body weight). Liquid Instillation delivers to the interior lung an amount of Infasurf that is approximately twice the amount of lung surfactant normally present in healthy newborn animals and 12 times the amount in healthy adults.¹ Thus, if at least 10% of the dose of 210 mg/kg body weight aerosolized Infasurf migrates to the deep lung it is expected the patient will become surfactant sufficient.

Repeat dosing will be administered if a positive effect was observed followed by subsequent deterioration of respiratory status. If a patient does not respond with sufficient benefit to the aerosolized Infasurf the attending physician can remove the patient from the aerosol trial and administer instilled Infasurf or other approved surfactant.

2.6 Compliance

The study will be conducted in compliance with Good Clinical Practices.

2.7 Study Population

Patients will be recruited who:

- (a) have a clinical diagnosis of RDS,
- (b) are receiving respiratory support: supplemental oxygen plus (a) nasal continuous positive airway pressure (NCPAP), or high flow nasal cannula (HFNC) or non-invasive ventilation (NIV) to assist breathing
- (c) are not intubated and receiving mechanical ventilation for respiratory failure.

3. OBJECTIVES AND PURPOSES OF THE TRIAL

For newborn infants born with a deficiency in lung surfactant because of prematurity or other causes of delayed lung maturation lung surfactant replacement therapy is life saving.^{2,3,4} The objective of this trial is to demonstrate that there is a group of patients who can benefit from surfactant replacement therapy with lower risk of administration complications and less discomfort by utilizing an alternative, safer administration technique – aerosolization.

Currently surfactant replacement therapy requires instillation of a liquid suspension into the airways. In order to instill into the airways it is necessary that an endotracheal tube be inserted and the surfactant administered through the endotracheal tube. A single dose may not be sufficient therapy and, if repeat dosing is likely or inevitable, a decision has to be made to either prolong the time of intubation or to remove the tube and possibly subject the patient to re-

intubation. One purpose of this trial is to determine if aerosolizing Infasurf provides an effective alternative for some patients that enable delivery of surfactant replacement therapy without subjecting them to the pain, discomfort and risk of endotracheal intubation or re-intubation.

The volume of the liquid instillation of the currently approved surfactants (2.5 to 4.0 mL/kg body weight) is larger than the total volume of the airways below the trachea which is 1 ml/kg body weight. Complications at administration are the physiologic consequences of two processes: (a) liquid obstruction of some airways, and (b) stimulation of irritant receptors in the lung. Liquid obstruction can produce transient low blood oxygen and high blood carbon dioxide, which together with neurally mediated irritant reflexes result in transient cardiopulmonary dysfunctions: cyanosis, tachycardia, bradycardia, hypotension, hypertension, airway obstruction and reflux of surfactant. Aerosolized delivery has the potential of minimizing both airway obstruction by liquid and the stimulation of irritant receptors in the lung.

Specifically the Objectives of the Trial are:

- (a) Document superiority of aerosolized of Infasurf to usual care in early RDS in preventing the need to intubate and instill a liquid surfactant suspension into the patient.
- (b) Show acute improvement in respiratory function by aerosolized Infasurf.
- (c) Document that aerosolized Infasurf is as safe as “usual care” for RDS patients.

4. TRIAL DESIGN

4.1 Efficacy endpoints

The primary efficacy endpoint will be the incidence of the requirement for endotracheal intubation and instillation surfactant to “usual care” over 72 hours, the time course for acute RDS.

Secondary efficacy endpoints will measure other clinical parameters that are indicative of lung surfactant sufficiency:

- (a) Incidence of death and/or bronchopulmonary dysplasia (defined as an oxygen requirement to maintain acceptable blood oxygen saturations) at 28 days or discharge, whichever comes first.
- (a) Severity of acute RDS measured by quantitation of oxygen supplementation and respiratory support from randomization to 72 hours of age or intubation and surfactant instillation, whichever comes first.
- b) Duration of acute RDS measured by duration of supplemental oxygen.
- c) Protection from acute lung injury as measured by the incidence of lung air leaks or pulmonary hemorrhage from randomization to 72 hours of age or intubation and surfactant instillation.

4.2 Trial Design

This will be a prospective, randomized unmasked study comparing Infasurf aerosolization to “usual care.” There will be a 1:1 patient assignment to each group.

4.3 Bias avoidance

Randomization codes predetermined using small, but variable, blocks to assure that each site will have approximately a 1:1 ratio of aerosolized and usual care participants. The study will be unblinded because it is impossible to blind staff to aerosolization of Infasurf. Visual evidence of Infasurf administration is obvious to all care givers both during and after the therapy. Also it is not ethically justified to subject the “usual care” group of fragile NICU patients with RDS to aerosolization with a saline placebo when there is only the potential for complications and none for benefit.

4.4 Trial Product

Infasurf (calfactant) is an FDA approved surfactant replacement drug. Repeated testing documents that aerosolization produces no change in its composition, biophysical or biologic activity.⁵ Aerosolization utilizes a Solarys® disposable nebulizer FDA approved for human use in patients on mechanical ventilation. The device has been modified so that the distal end is imbedded in a “pacifier like” modification that insures the tip cannot be obstructed by oral tissues and protects the oral tissues from abrasion by the tip of the device. The Infasurf is aerosolized into the oropharynx in micro-droplets of 3 to 100 microns diameter rather than into the bias flow at the nose.

4.5 Duration

Patients are eligible for randomization to aerosolized Infasurf therapy or “usual care” to 12 hours of age if not treated with instilled surfactant in the first hour of life; or to 24 hours of age if treated with instilled surfactant at birth (≤ 1 hour of age). Aerosolized patients may receive up to 3 aerosol treatments. For the “Usual Care” there is no “participation” in any intervention only extraction of data from medical record.

Data will be extracted from the medical record until day 28 of life or discharge from the hospital, whichever occurs first.

No long term follow-up is planned for this study. No long term harm has been identified in the pivotal studies used for regulatory approval of any surfactant.^{2, 3, 4}

4.6 Stopping Rules

Individuals: Aerosolization will require the usual bedside monitoring by NICU devices and personnel appropriate for all patients in the first hours of life with significant respiratory difficulty. Any patient, who in the judgment of the clinical care team, is experiencing an adverse event due to the aerosolization will have it stopped and not restarted. Taking appropriate remedial steps to resolve an adverse event will be the responsibility of the patient’s clinical care team. The patient will not receive additional aerosol therapy if dosing is discontinued due to an adverse event.

Sites. Following an adverse event resulting in discontinuation of aerosol therapy, recruitment by that site will automatically be suspended.

The Principal Investigator (or a co-investigator) will notify the sponsor within 24 hours of the adverse event. The Sponsor will notify the Study Chair and the Chair of the Data Monitoring and Safety Committee (DMSC) within 24 hours of receiving notification.

The site will not re-start recruiting to the study until the site P.I., the Study Chair and the Sponsor decide that appropriate remediation, if necessary, has been achieved.

Any adverse event during aerosolization will be reviewed by the NICU Medical Director at the site within 24 hours of occurrence. S(he) shall contact and consult with the Study Site P.I. and after that review either allow the study to continue recruiting or suspend the study. In either case the local IRB and the Medical Director of the Sponsor will be notified within 24 hours. If the study is suspended it will not be restarted until the NICU medical director, the site P.I., the local IRB, and the Sponsor have all approved the decision to restart the trial at that site.

In addition, if the study is suspended at any one site the Sponsor will notify the P.I. at all other participating sites and the national and all local IRBs. Any local IRB, site P.I. or the Sponsor can suspend the study at any or all of the other participating sites. If suspended at other sites restarting will require prior approval by the local IRB and P.I. and the Sponsor.

Entire Trial: The Study Chairman, the DSMB chair and the Sponsor will confer upon receiving notification of any adverse event resulting in discontinuation of aerosol therapy with 24 hours. If any one of the three judges that the welfare of patients is best served by suspending recruitment to the trial the Sponsor shall immediately notify all the sites that recruitment for the study has been suspended and the reason for the suspension.

Within 5 days the Principal Investigator of the site where the adverse event occurred will submit a full description of the adverse event along with relevant data from the patient's medical record. The PI will provide an assessment and recommendations with the summary and the data.

Upon receipt of report from the site PI the Study Chair and the DMSC shall separately review the communication from the site P.I. The Study Chair and the Chair of the DMSC will hold a teleconference to reach a consensus to advise the Sponsor to:

- (a) Stop the trial for the safety of patients.
- (b) Suspend the trial until the cause of the adverse event is identified and remedied.
- (c) Suspend the trial at the site of the adverse event only until a cause is remedied.
- (d) Restart the trial at the site and continue the trial at the other sites.

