- 2) a subsequent deterioration in respiratory function, and
- 3) no adverse event during the initial dose.

Usual Care: There will be no protocol driven interventions in the usual care group. Use of pacifiers as tolerated in these patients is encouraged to decrease the incidence of loss of continuous airway pressure through the mouth.

Sham therapy has not been included because it cannot produce an effective masking of treatment assignment to care givers because of both the presence of residual Infasurf in the mouth and stomach and there is a reliable decrease in inspired oxygen requirement by the end of aerosolized Infasurf therapy.

Separation of the effect of additional gas infusion derived from aerosolized Infasurf effect by sham treatment is unnecessary. Pressure in the airway is set by the nasal therapy and that therapy will be adjusted, if necessary, to maintain the airway pressure ordered by the supervising provider. The tidal volume of spontaneous breathing participants is affected only by the airway pressure not by the volume of bias flow. Usual care patients will have the positive airway pressure set and adjusted as their respiratory status requires by their supervising provider.

The decision not include a sham procedure was also based on the concern of interrupting and/or modifying ongoing respiratory support in fragile newborns with RDS to implement the sham. Such an intervention has no reasonable expectation of benefit for the subject but does have some potential for adverse consequences. There will be no protocol driven interventions in the usual care group.

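### Section 4.6 gives two incompatible site-suspension rules for an adverse event that ends aerosol, and does not say how its restart approvals fit together

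*Combined protocol and SAP*

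**What the plan says.** Section 4.6 (Stopping Rules) handles an adverse event at three levels.

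- **Individuals.** "The patient will not receive additional aerosol therapy if dosing is discontinued due to an adverse event".
- **Sites, automatic rule.** After an adverse event that ends aerosol therapy, "recruitment by that site will automatically be suspended". The site then stays closed "until the site P.I., the Study Chair and the Sponsor decide that appropriate remediation, if necessary, has been achieved".
- **Sites, director's review.** "Any adverse event during aerosolization will be reviewed by the NICU Medical Director at the site within 24 hours of occurrence". The director consults the site P.I. and may "after that review either allow the study to continue recruiting or suspend the study". A suspended study stays closed at that site "until the NICU medical director, the site P.I., the local IRB, and the Sponsor have all approved the decision to restart".
- **Entire Trial.** After any event that ended aerosol therapy, the Study Chair, the DSMB chair and the Sponsor confer, and any one of them can have recruitment suspended across the trial. The site P.I. sends a full report within 5 days. The Study Chair and the DMSC Chair then agree advice to the Sponsor; one of the four options is to restart the site while the other sites continue.

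Two other sections bear on the individual infant. Section 6.1 lists three conditions for re-dosing, the third being "no adverse event during the initial dose". Section 5.3, item 3, withdraws an infant from further study interventions after an event that required aerosol to be discontinued.

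**The concern.** The automatic rule and the director's review are both written for the site where the event occurred, and neither refers to the other. If the same event triggers both, a site that follows one paragraph to the letter can breach the other. The same question arises at restart, because the two paragraphs name different approvers.

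These are the site-level safety controls of an unblinded multicenter trial in newborns. If they are unclear, a site may keep recruiting when another paragraph says that it is closed, or reopen without an approval that another paragraph requires. Either leads to protocol deviations and to disputes with the local IRB at the moment when the rule is needed.

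**Working it through.** No calculation underlies the rules, so the check sets the texts side by side.

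**1. Suspension (4.6, Sites)**

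| | Automatic rule | Director's review |
|---|---|---|
| Trigger | Adverse event that ended aerosol | Any adverse event during aerosolization |
| Who decides | No one; it follows from the event | NICU medical director, after consulting the site P.I. |
| Result | Site recruitment suspended | Recruitment continues or is suspended |

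An event that ends a dose is an event during aerosolization, so every event in the first column is also in the second. If the director chooses suspension, both rules are met. If the director allows recruiting to continue, the automatic rule is broken; if the site is closed regardless, the director's choice has no effect. One branch of the second rule is therefore incompatible with the first.

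Reading the two in sequence, with automatic closure lasting until the director's review, does not help. The automatic rule has its own condition for reopening, and the director is not one of its parties.

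**2. Restart (4.6, Sites and Entire Trial)**

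| Party | After automatic suspension | After director's review | Entire Trial |
|---|---|---|---|
| Site P.I. | Decides | Approves | Reports |
| Sponsor | Decides | Approves | Receives advice |
| Study Chair | Decides | – | Advises |
| NICU medical director | – | Approves | – |
| Local IRB | – | Approves | – |
| DMSC Chair | – | – | Advises |

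Only the site P.I. and the Sponsor are on both lists of approvers. The second list applies whenever the study is suspended at the site and is not limited to suspensions ordered by the director. The Entire Trial text does not say whether its advice comes before, replaces or adds to either list. A site that relies on the first list alone could reopen without the local IRB approval that the second requires.

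**3. Re-dosing (6.1 item 3 against 4.6 and 5.3)**

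| Case | 6.1 item 3 | 4.6 and 5.3 | Applied together |
|---|---|---|---|
| Event in the initial dose, dose completed | Not met | No bar | No re-dose |
| Uneventful first dose, second dose stopped for an event | Met | Barred | No third dose |
| Uneventful first dose, event in second dose, dose completed | Met | No bar | No bar from either text |

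The triggers differ in the first two cases, but applying both texts gives one answer each time.

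**4. How many events**

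- Enrolment (9.1): up to 200 + up to 458 = at most 658. With 1:1 allocation, 658 / 2 = 329 aerosol infants at most.
- The documents give no rate for doses stopped because of an adverse event. Assumed rates of 1%, 2% and 5% of infants give 329 × 0.01 = 3.3, 329 × 0.02 = 6.6 and 329 × 0.05 = 16.45, so about 3, 7 and 16.
- Section 2.3 reports over 30 pilot patients with no discontinuation for interference with breathing. Taking 0 of 30, the one-sided 95% upper limit is 1 − 0.05^(1/30) = 0.095. The pilot result is therefore compatible with anything from zero to about 9.5%, and it covers only that one cause.

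**The case against.** The best defence is that a two-tier scheme was intended: automatic suspension for events that end aerosol, and the director's discretion for the rest. The Individuals paragraph stops aerosol for events judged to be due to it, so an event during dosing need not end the dose. The Entire Trial paragraphs also treat discontinuation events as a class of their own. This is a plausible intent, and it would remove the suspension conflict. But it is not written: the director's review covers any adverse event during aerosolization, without exception. It would also mean that the automatic suspension reopens on a list without the local IRB, while the discretionary one requires it.

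A reader might go further than the documents allow in three ways.

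- **That the restart lists contradict each other.** They do not. Each is a necessary condition, neither claims to be sufficient, and a site could satisfy both. One group judges remediation and the other approves the restart. What stands is that their relation is unstated.
- **That 6.1 and 4.6 contradict each other on re-dosing.** They do not. A list of indications does not override a bar, and 5.3 repeats the bar. A different answer arises only for someone who reads one section alone.
- **That sites could diverge unchecked.** After every discontinuation event the Study Chair, the DSMB chair and the Sponsor confer, and the Sponsor is notified under either site paragraph. This limits divergence but does not tell the site which paragraph governs.

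**Conclusion.** The point holds for site suspension: read literally, 4.6 directs opposite actions for an adverse event that ends aerosol if the director allows recruiting to continue. For restart, the finding is an unstated relation between two lists and a separate advisory route. For re-dosing, it is a minor lack of cross-reference.

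The number of affected events is unknown. A reader might take 3 to 16 as a forecast, but it rests on assumed rates of 1% to 5% and on the maximum of 329 aerosol infants. The pilot experience allows a true figure near zero and does not exclude the assumed rates. A single event is enough to bring both site rules into play. The endpoint, sample size, power and alpha are unaffected. The passages should be reconciled because these are safety rules and the change is small; no view is taken here on which rule should apply.

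**What to change.** Reconcile the site paragraphs of 4.6 with each other and with the Entire Trial paragraphs, so that:

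1. each type of event (ending aerosol, or not) has one suspension rule, with its decision-maker named;
2. each suspension has one stated set of restart approvers, and if the two present lists are meant to be cumulative, the text says so;
3. the advice from the Study Chair and the DMSC Chair is given a stated place in that sequence.

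As a minor addition, cross-reference 6.1 item 3 with 4.6 and 5.3 and state one reconciled re-dosing rule that covers every dose, including an event in a repeat dose that did not end it, where these texts set no bar.

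The sponsor and clinical leads decide which rules apply. The cost is protocol wording only; no analysis or sample-size figure changes.
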